## **REGULATORY FRAMEWORK:**

Please indicate all that apply:

	DOD (Department of Defense)
	DOE (Department of Energy)
	DOJ (Department of Justice)
	ED (Department of Education)
	EPA (Environmental Protection Agency)
	FDA (Food and Drug Administration)
	HHS (Department of Health and Human Services)
	Other:

Is this a clinical trial under ICH-GCP E6?  Yes  No

If yes, please confirm that the research team is familiar with and agrees to comply with the investigator requirements cited in ICH-GCP E6.  Yes  No

ICH-GCP E6 can be accessed by copying and pasting this URL into your browser:  
<http://www.fda.gov/downloads/Drugs/Guidances/ucm073122.pdf>

# DIDIT: Diuretic/Cool Dialysate Trial

## 1. Objectives

Each year in the United States, approximately 100,000 people start maintenance dialysis therapy suffering high mortality rates, frequent hospitalizations, and marked decline in quality of life. The overarching aim of the “**Diuretic/Cool Dialysate Trial**” (DIDIT) is to improve outcomes of incident hemodialysis (HD) patients by recognizing the importance of residual renal function (RRF). This pilot study will demonstrate the feasibility of loop diuretic (bumetanide) use and/or cool dialysate, and will obtain preliminary information that will inform future examination into whether these interventions will slow the rate of RRF decline in HD, improve quality of life, and reduce overall mortality.

The proposed pilot study challenges the current widespread paradigm of discontinuing loop diuretics when initiating chronic HD and/or maintaining the dialysate at a constant temperature of 37 °C for all patients.

**Specific Aim:** We aim to conduct a pilot randomized controlled trial (RCT) to assess feasibility and safety, and to inform the design of a full-scale trial of bumetanide and/or cool dialysate using a two-by-two factorial design, compared to usual care.

The long-term goals of this proposed work are to optimize survival, health-related quality of life (HRQOL) and other outcomes of HD patients by providing them a low dose of a loop diuretic and by lowering the dialysate temperature at the start of their transition to dialysis therapy. The design will permit a rapid scaling-up of the interventions to a larger clinical trial since the incremental dialysis prescription takes advantage of resources and personnel that are readily available. This pilot study will substantially accelerate our ability to address fundamental issues in the care of this population, which is burdened by low HRQOL and can change the current paradigm and practice pattern.

**Hypothesis:** Use of bumetanide and/or cool dialysate during the first six months of HD will slow the rate of RRF decline, decrease inflammation and oxidative stress, improve HRQOL and decrease mortality. To explore this hypothesis we propose to conduct a pilot RCT.

## 2. Background

Many clinical trials have examined the extent to which outcomes could be improved in the prevalent dialysis population. However, incident HD patients have been largely overlooked despite their high mortality, morbidity and marked decrements in HRQOL. This proposal addresses the gap of care in incident HD patients by focusing on maintaining RRF, one of the strongest predictors of survival and HRQOL in the first year of dialysis therapy.

Many different factors have been implicated in the decline of RRF in HD, and therefore many different therapeutic strategies have been suggested for the preservation of RRF in these patients. In this study, we intend to evaluate two different therapeutic approaches: the use of a loop diuretic (bumetanide) and/or the use of cool dialysate during the HD session.

## DIDIT: Diuretic/Cool Dialysate Trial

Diuretic therapy remains the cornerstone of managing fluid overload. The role of diuretics in managing HD patients is not yet clearly defined (1). Diuretics can be used to minimize RRF loss in chronic HD patients (1). More specific loop diuretics are not nephrotoxic, confer better fluid balance, maximize urine production, allow less aggressive ultrafiltration and are associated with decreased cardiac mortality (1, 2). The DOPPS study verified that loop diuretics are the most often prescribed diuretics to chronic HD patients (2). In clinical practice, many patients begin HD chronically using small doses of a loop diuretic, but since there is little evidence that these are beneficial, their use is suspended when the volume of residual diuresis is reduced to minimum values.

While currently not the standard of care in the US, cool dialysate may confer significant survival benefits. Cool dialysate has been associated with decreased intradialytic hypotension which may minimize kidney injury and slow RRF decline. The current US paradigm is to maintain dialysate temperature according to physician's discretion, usually at 37 °C. Cool dialysate may decrease inflammatory and oxidative stress from HD therapy, and thus minimize kidney injury, slow the decline of RRF, and decrease morbidity and mortality. This important strategy of preserving RRF is not routinely applied to HD patients.

The use of bumetanide is also not currently the standard of care, but additionally may provide survival benefits by minimizing RRF loss. Specifically, bumetanide is not nephrotoxic, confers better fluid balance, maximizes urine production, may allow less aggressive ultrafiltration and is associated with decreased cardiac mortality.

Each year in the US approximately 100,000 people begin chronic dialysis and 80,000 die resulting in the growth of the prevalent population which now exceeds 400,000 patients on chronic dialysis. Prevalent HD patients have a mortality rate of 20% per year. Even more disconcerting is that during the first six months of therapy the annualized mortality is 35-40%. Although many clinical trials have examined the extent to which outcomes could be improved in the prevalent dialysis population, incident HD patients have been largely overlooked despite their high mortality, morbidity and marked decrements in HRQOL. This proposal addresses the crisis of care in incident HD patients by focusing on maintaining RRF, one of the strongest predictors of survival and HRQOL in the first year of dialysis therapy.

### **3. Study Design**

This pilot RCT will demonstrate the feasibility and safety of performing a large scale study of diuretic use and/or cool dialysate by examining recruitment, retention, and key outcomes. This study will further assess whether the use of a diuretic compared to non-use of a diuretic (placebo) and/or the use of cool dialysate (35.5 °C) compared to 37 °C for up to 6 months will improve RRF, improve HRQOL and reduce hospitalizations. by randomizing 20 chronic hemodialysis patients from DCI centers in the greater Albuquerque area, to either bumetanide and cool dialysate randomized in a two-by-two factorial distribution.

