# DIDIT: Diuretic/Cool Dialysate Trial

No Diuretic (placebo) and 37°C dialysate	No Diuretic (placebo) and 35.5°C dialysate
Diuretic and 37°C dialysate	Diuretic and 35.5°C dialysate

The study sample will be selected using an approach to limit drop-out while enhancing generalizability and the main analysis will be intention-to-treat. *Considering the intervention cannot be double-blinded, we have made efforts to reduce bias by using objective outcomes and blinding the assessment of patient-reported outcomes.* Subjects will be recruited for 18 months. An additional 6 month period will be used to complete the intervention in the last subjects and they will be re-assessed at month 8 for an end of study evaluation. The recruitment and participation parameters for development of this formal RCT will assess whether the large scale study can meet enrollment criteria and target timelines, and whether patients can be maintained on the study protocol without safety concerns.

In this pilot study we will assess as primary patient outcomes:

- The change in RRF over 6 months
- The association of cool dialysis and/or diuretic with inflammation
- The association of cool dialysis and/or diuretic use with acute kidney injury (AKI) biomarkers.

The secondary patient outcomes will be:

- Change in HRQOL
- Time to first-hospitalization.

Being a pilot study, our focus is on assessing whether changes in RRF can be detected with the proposed technique (urinary creatinine and urea clearance). Biomarkers of inflammation and AKI will be collected to supplement the functional measurement of renal filtration and as surrogate biomarkers of benefit or safety (e.g. nephrotoxicity) that can be monitored in the large scale study.

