## 5. Number of Subjects

Up to 50 patients may be recruited/consented for this study.

It is unknown, at this time, how many eligible subjects will need to be approached in order to attain the desired number of study participants. We will continue to recruit until 20 patients have been followed to completion post protocol modification.

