# DIDIT: Diuretic/Cool Dialysate Trial

## 18. Risks to Subjects

**Hemodialysis:** may be associated with complications. Hemodialysis can lead to low blood pressure (25% of all dialysis sessions) which may result in abdominal discomfort, nausea, vomiting, muscle cramps, dizziness and anxiety. In addition, hemodialysis can lead to bleeding, tachycardia and other abnormal heart rhythms, electrolyte imbalances, clotting or infection of the vascular access, and rarely, death. ***However, the risks associated with HD would be present whether or not the patient chooses to participate in this study.*** It is unknown whether use of diuretic and cool dialysate will increase or decrease the risk of these complications.

**Cool dialysate (35.5°):** The most common complication for patients dialyzed with cool dialysate is feeling colder, and if severe, they may develop shivering.

Patients will be monitored for patient comfort during dialysis to assess cold intolerance that may occur with cool dialysate. If these symptoms are observed, then the PI will determine whether this is a safety endpoint.

**Bumetanide:** Muscle cramps, severe dizziness, and hearing changes, like ringing in the ears, are the most common side effects of bumetanide (1.1%). A very serious allergic reaction to this drug is also rare.

Patients will be monitored for hypersensitivity reaction or musculoskeletal symptoms to determine tolerability of patients to the diuretic.

**Psychological:** Participants may be asked some questions of a personal nature. They are free to decline to answer any question at any time.

**Loss of Privacy:** Participation in research may involve a loss of privacy. Steps will be taken to mitigate the risk related to confidentiality of study data.

**Pregnancy:** The risk(s) of cool dialysate and/or Bumetanide on a developing fetus are unknown; therefore, subjects who are pregnant or actively planning to become pregnant in the next 8 months will not be allowed to participate in this study.

Subjects of child-bearing potential will have a pregnancy blood test done prior to study randomization. Subjects that refuse pregnancy testing will not be allowed to participate in this study.

**Nursing Mothers:** It is not known whether Bumetanide is excreted in human milk. Breast feeding should not be undertaken while the participant is on this drug. Breast feeding females will not be allowed to participate in this study.

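### Section 3 promises to demonstrate feasibility and safety, but no threshold is set, about 10 patients receive each intervention, and cold symptoms become a safety endpoint only if the PI so decides afterwards

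*Combined protocol and SAP*

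**What the plan says.** Section 3 sets the purpose: "This pilot RCT will demonstrate the feasibility and safety of performing a large scale study of diuretic use and/or cool dialysate". It adds that the pilot will assess "whether patients can be maintained on the study protocol without safety concerns". Section 1 also uses the verb *demonstrate* for feasibility, but its Specific Aim is milder: "assess feasibility and safety, and to inform the design of a full-scale trial of bumetanide and/or cool dialysate using a two-by-two factorial design". Section 7 lists estimating recruitment and retention rates and collecting preliminary data on AEs and SAEs. Section 13 says the proportions recruited and retained will be estimated.

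On numbers, Section 3 plans to proceed "by randomizing 20 chronic hemodialysis patients from DCI centers in the greater Albuquerque area", and Section 13 also refers to 20 randomized. Section 7 says 25 randomized. Section 5 allows up to 50 consented and says: "We will continue to recruit until 20 patients have been followed to completion post protocol modification". Recruitment is to last 18 months.

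On safety, Section 14 provides an independent Investigator Monitor who may recommend stopping or redesign and will terminate the study if patients are put in jeopardy. No event type, count or rate is attached. Section 18 says patients will be watched for cold intolerance and continues: "If these symptoms are observed, then the PI will determine whether this is a safety endpoint". Section 13 names analyses for number of hospitalizations, days in hospital and time to first hospitalization. It names none for the other harms in Section 18, for SAEs or for death.

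**The concern.** To demonstrate something, a study must be able to fail a stated test. Here no recruitment, retention, adherence or adverse-event value is tied to a conclusion, so the word promises more than the design can deliver. The pilot exists to inform a larger trial. A clean record in a handful of patients, reported under a plan that said it would demonstrate safety, could be read as reassurance that the data do not contain.

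The rule for cold symptoms adds a route to bias. These are the complications Section 18 names for cool dialysate. Section 3 concedes that the intervention cannot be double-blinded. Since the diuretic has a placebo, dialysate temperature is evidently the open factor. Deciding after the event whether a symptom is an endpoint, with the arm probably known, allows the same symptom to be treated differently in the cool and 37 °C arms.

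**Working it through.** **Inputs.** 20 randomized (Sections 3 and 13) or 25 (Section 7); two-by-two factorial (Sections 1 and 3); up to 50 consented (Section 5); 1.1% for the most common bumetanide effects and low blood pressure in 25% of dialysis sessions (Section 18); 95% confidence level (Section 13, for retention and mean change). *Assumption:* equal allocation, so half of those randomized receive each intervention.

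**The plan's own figure.** Section 13 gives retention to within ±0.18 with 20 patients and does not state the retention assumed. The usual half-width is 1.96 × √(p(1−p)/n).
- p = 0.80, n = 20: 1.96 × √(0.16/20) = 0.175, which rounds to 0.18. The figure reproduces.
- p = 0.50 gives ±0.219; p = 0.90 gives ±0.131.
- If 16 of 20 are retained, the exact 95% interval is 56% to 94%. The plan labels no value in that range inadequate.

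**What zero events would show.** For 0 events in n exposed, the exact two-sided 95% upper limit is 1 − 0.025^(1/n).

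| Exposed (n) | Basis | Upper limit |
|---|---|---|
| 5 | one cell of 20 | 52.2% |
| 10 | one factor, 20 randomized | 30.8% |
| 12 | one factor, 25 randomized | 26.5% |
| 13 | one factor, 25 randomized | 24.7% |
| 25 | one factor, if all 50 consented were randomized | 13.7% |

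The one-sided 95% limit for 0/10 is 1 − 0.05^(1/10) = 25.9%. Each limit is for one type of harm. The last row is an extreme, because some consented patients will fail the urine-collection criterion. To put the two-sided limit below 10% with no events, 36 exposed patients are needed: ln 0.025 / ln 0.90 = 35.01, rounded up.

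**Chance of seeing at least one case in 10 exposed,** 1 − (1 − r)^10:
- r = 1.1% (Section 18): 10.5%
- r = 5% (illustrative): 40%
- r = 10% (illustrative): 65%

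**How harms are captured and judged.** The adverse-event list in Table 1 (Section 12) includes hospitalization, mortality, hypotensive episodes and access events. It does not list cold intolerance, shivering, cramps, dizziness, hearing changes or hypersensitivity, although Section 18 names all of these or says they will be monitored. Section 14 asks for relationship to hemodialysis frequency, the diuretic and iohexol; cool dialysate is not on that list.

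**The case against.** The best reply is that this is a pilot and most of the text already treats it as one. Sections 1, 7 and 13 speak of assessing, estimating and collecting preliminary data, so the overstatement is one verb in Section 3 and one in Section 1. That is fair, and it makes the rewording easy, but it does not touch the rule in Section 18 or the missing harm analyses.

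A reader might infer several stronger things that the documents do not support.

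- *That no observable result could count against safety.* Section 14's monitor reviews all data and can terminate the study. That provision is unquantified and protects participants during the trial rather than guiding progression, but termination would plainly count.
- *That the recruitment target is met by construction.* Recruiting until 20 complete does not guarantee success: the 18-month window and the limit of 50 consents can both bind. The outputs are recruitment and retention rates, and a slow pace or heavy drop-out would show in them.
- *That there is no adverse-event analysis.* Table 1 lists hospitalization as an adverse event and Section 13 analyses it in three ways. Section 3 also makes AKI biomarkers primary outcomes and possible nephrotoxicity markers. Section 13's provision for discrete variables might be stretched to other events, but it names none, and logistic or Poisson regression gives no finite estimate of a group effect when one group has no events.
- *That a clean record is likely whatever the truth.* This holds for effects near 1.1%. It does not hold for cramps and dizziness, which Section 18 also links to low blood pressure in 25% of sessions. Nor does it hold for death: reading Section 2's 20% a year for prevalent patients and 35–40% annualized for the first six months as yearly risks, the chance of at least one death among 10 patients in six months is 1 − 0.80^5 = 67% up to 1 − 0.60^5 = 92%. It would be lower given the life-expectancy exclusion.

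It is also fair that nothing in Section 18 says cold symptoms would go unrecorded. The objection there is to choosing endpoint status afterwards.

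**Conclusion.** The point holds in this form. The plan claims to demonstrate feasibility and safety, pre-specifies no progression or safety threshold, and exposes about 10 patients to each intervention. For any single harm with no events, the data would remain compatible with a risk of up to 31% (two-sided exact 95%, equal allocation of 20), or about 25–26% if 25 are randomized. The limit falls further if more than 20 are randomized to obtain 20 completers. Feasibility can be estimated and safety described; neither can be demonstrated against a standard that is not stated. The most consequential single item is the PI's after-the-event choice about cold symptoms. The inference that temperature is the unblinded factor rests on Section 3's concession and the existence of a placebo.

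**What to change.** 1. **Sections 3 and 1.** In Section 3, replace the claim to demonstrate both with *estimate feasibility and describe safety*. Bring the matching verb in Section 1 into line.
2. **Section 18.** Remove the PI's choice of endpoint after the event. Record and count cold intolerance, shivering and the named bumetanide effects in the same way in all four arms, and list them in Table 1. Judge causality separately, and add cool dialysate to the relationship assessment in Section 14.
3. **Section 13.** For each factor, report the number and proportion with each named harm, any SAE and death, with exact 95% limits. Where no event occurs, give the upper limit and draw no conclusion of safety from it.
4. **Numbers.** Reconcile 20 randomized, 25 randomized and 20 completers. Any progression values for recruitment and retention are the investigators' choice and should be fixed before analysis. The plan's implied pace, 20/18 = 1.1 per month, should not be used as a pass mark. It conflicts with 25/18 = 1.4 and treats completers as randomized. A trial recruiting exactly on plan would also fall below it about 47% of the time (Poisson, mean 20, fewer than 20).

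The cost is protocol and analysis wording, a few extra items on the adverse-event form and one table. No patients, visits or treatment changes are needed. The downside is a weaker safety claim.

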# DIDIT: Diuretic/Cool Dialysate Trial

No Diuretic (placebo) and 37°C dialysate	No Diuretic (placebo) and 35.5°C dialysate
Diuretic and 37°C dialysate	Diuretic and 35.5°C dialysate

The study sample will be selected using an approach to limit drop-out while enhancing generalizability and the main analysis will be intention-to-treat. *Considering the intervention cannot be double-blinded, we have made efforts to reduce bias by using objective outcomes and blinding the assessment of patient-reported outcomes.* Subjects will be recruited for 18 months. An additional 6 month period will be used to complete the intervention in the last subjects and they will be re-assessed at month 8 for an end of study evaluation. The recruitment and participation parameters for development of this formal RCT will assess whether the large scale study can meet enrollment criteria and target timelines, and whether patients can be maintained on the study protocol without safety concerns.

In this pilot study we will assess as primary patient outcomes:

- The change in RRF over 6 months
- The association of cool dialysis and/or diuretic with inflammation
- The association of cool dialysis and/or diuretic use with acute kidney injury (AKI) biomarkers.

The secondary patient outcomes will be:

- Change in HRQOL
- Time to first-hospitalization.

Being a pilot study, our focus is on assessing whether changes in RRF can be detected with the proposed technique (urinary creatinine and urea clearance). Biomarkers of inflammation and AKI will be collected to supplement the functional measurement of renal filtration and as surrogate biomarkers of benefit or safety (e.g. nephrotoxicity) that can be monitored in the large scale study.

## 4. Inclusion and Exclusion Criteria

Hemodialysis patients required for this pilot project will be identified from the patient population treated at DCI centers in the greater Albuquerque area. The average age of patients at the study sites is approximately 58 years, and the population is roughly split between genders and is racially diverse. Approximately 95% of the dialysis clinic population speak or understand English. The study site population demographics are similar to those in the Southwestern region and include more Hispanic patients than nationally. NIH standards for collecting data will be maintained, and when providing informed consent the investigators will rely on two separate questions for patients to self-identify ethnicity and race (in that order).

## DIDIT: Diuretic/Cool Dialysate Trial

The study is open to all volunteers, irrespective of gender, race, ethnicity, or sexual preference. Women will constitute nearly half of the expected sample, and minorities are well represented. This is not an NIH-defined Phase III Clinical Trial, but analyses will be conducted at the conclusion of the study to determine whether the intervention affected women or men or members of minority groups and their subpopulations differently.

Consented participants must have adequate RRF (See second exclusion bullet below) to complete this study. Adequate RRF is determined by the result of the first 24-hour urine collection. The participant's RRF will either allow them to continue or exclude them from the study.

- Participants with adequate RRF will be randomized to one of the four study arms listed above.
- The randomization process may take up to 7 days.
- Randomized participants will have any ordered diuretics discontinued before they begin taking the “study drug”
- There is no “taper” or “time delay for stopping their diuretic and starting the “study drug”

